7.2.2 Success Criteria for Secondary Immunogenicity Objectives

CBER criteria for seroconversion at Day 43 will be evaluated for both age cohorts as defined below. Results collected at Day 22 will also be evaluated against the CBER criteria for both age cohorts.

Immunogenicity according to CBER in subjects 18 - < 65 years of age

The aH5N1c vaccines immunogenicity will be evaluated in subjects 18 to < 65 years of age, using the following measurements according to the current CBER criteria for the adult population (CBER 2007):

- The lower bound of the adjusted two-sided 95% CI for the percentage of subjects achieving an HI antibody titer $\geq 1:40$ should meet or exceed 70%.
- The lower bound of the adjusted two-sided 95% CI for the percentage of subjects achieving seroconversion for HI antibody should meet or exceed 40%.

Immunogenicity according to CBER in subjects ≥ 65 years of age

The aH5N1c vaccine immunogenicity will be evaluated in subjects ≥ 65 years of age, using the following measurements according to the current CBER criteria for the ≥ 65 years of age population (CBER 2007):

- The lower bound of the adjusted two-sided 95% CI for the percentage of subjects achieving an HI antibody titer $\geq 1:40$ should meet or exceed 60%.
- The lower bound of the adjusted two-sided 95% CI for the percentage of subjects achieving seroconversion for HI antibody should meet or exceed 30%.

To assess CHMP criteria (CPMP/BWP/214/96), the estimate of proportions of subjects with HI titer $\geq 1:40$ and proportions of subjects achieving seroconversion and GMR will be compared against threshold as follows:

Criteria for subjects 18 to 60 years of age:

- The percentage of subjects with seroconversion in HI antibody is $>40\%$;
- The GMR is >2.5 ;
- The percentage of subjects achieving an HI titer $\geq 1:40$ is $>70\%$.

For subjects > 60 years of age:

- The percentage of subjects with seroconversion in HI antibody is $>30\%$;
- The GMR is >2.0 ;
- The percentage of subjects achieving an HI titer $\geq 1:40$ is $>60\%$.

7.2.3 Success Criteria for Secondary Efficacy Objectives

Not applicable.

7.2.4 Success Criteria for Safety Objectives

Not applicable.

7.3 Analysis Sets

7.3.1 All Enrolled Set

All screened subjects who provide informed consent and provide demographic and/or baseline screening assessments, regardless of the subject's randomization and treatment status in the study.

7.3.2 Exposed Set

All subjects in the All Enrolled Set who receive a study vaccination.

7.3.3 Full Analysis Set (FAS) Immunogenicity Set

All subjects in the All Enrolled Set who:

- actually receive at least one dose of study vaccination, and
- provide at least one evaluable serum sample at relevant timepoints.

FAS will be defined by timepoint and objective, for example:

- FAS1 (applicable to lot-to-lot objective, GMT at Day 43, the percentage of Subjects achieving an HI antibody titer $\geq 1:40$ at Day 43) will include all subjects who received at least one dose of study vaccine and provide at least one evaluable serum sample at Day 43.
- FAS2 (applicable to CBER criterion on seroconversion or significant increase) will include all subjects who received at least one dose of study vaccine and provide at least one evaluable serum sample at Day 1 AND Day 43.

More details will be provided in the statistical analysis plan.

FAS will be analyzed "as randomized" (i.e., according to the vaccine a subject was designated to receive, which may be different from the vaccine the subject actually received).

7.3.4 Per Protocol Set (PPS), Immunogenicity Set

All subjects in the FAS Immunogenicity Set who:

- Are not excluded due to reasons (see [section 7.3.8](#)) defined prior to unblinding or analysis.

Examples for subjects excluded due to other reasons than major protocol deviations are:

- subjects who withdrew informed consent.

Similarly to FAS, PPS will also be defined per objective and timepoint.

Exclusions will be considered by objective/time point, i.e., sometimes not all data of a subject but only part of the subject's data will be removed from the PPS analysis.

7.3.5 Safety Set

Safety Set (solicited adverse events and other solicited adverse events)

All subjects in the Exposed Set who:

- Provide post vaccination solicited AE data.

Safety Set (unsolicited adverse events)

All subjects in the Exposed Set who:

- Have post-vaccination unsolicited AE records.

Safety Set (overall)

All subjects in the Exposed Set who:

- Have either post-vaccination solicited or unsolicited AE records.

Subjects will be analyzed as "treated" (i.e., according to the vaccine a subject received, rather than the vaccine to which the subject may have been randomized).

7.3.6 Other Analysis Sets

Not applicable.

7.3.7 Subgroups

Subgroup analyses also will be performed by stratifying the study population as appropriate for immunogenicity or safety parameters, as further detailed in the Statistical Analysis Plan (AP):

- Subjects stratified by baseline HI titer $<1:10$ or $\geq 1:10$
- Subjects with and without seasonal influenza vaccine in the last 12 months
- Subjects by age (CBER and CHMP defined)
- Subjects stratified by age: 18-49, 50-64, 65-74, over 75
- Subjects by race

- Subjects by sex
- U.S. subjects and non U.S. subjects

7.3.8 Protocol Deviations

A protocol deviation is any change, divergence, or departure from the study design or procedures of a study protocol. A protocol deviation may be a reason to remove data from an analysis set at the time of analysis. Reportable (major) protocol deviations will be defined as exclusionary from the analysis according to protocol objectives and endpoints, which will be specified in the statistical analysis plan. In some cases exclusion of data may be due to a reason other than a protocol deviation, e.g. early termination.

7.4 Analysis Plan

7.4.1 Analysis of Demographic and Baseline Characteristics

Descriptive statistics (mean, standard deviation, median, minimum and maximum) for age, height and weight at enrollment will be calculated by overall and by vaccine group.

Distributions of subjects by sex, ethnicity, race and previous influenza vaccination (in the past 12 months) will be summarized overall and by vaccination group.

7.4.2 Analysis of Co-Primary Objectives

For lot-to-lot consistency, the following equivalence hypotheses will be tested simultaneously:

$$H_0: (\mu_{\text{lot A}} - \mu_{\text{lot B}}) \leq -0.176 \text{ or } (\mu_{\text{lot A}} - \mu_{\text{lot B}}) \geq 0.176 \text{ or} \\ (\mu_{\text{lot A}} - \mu_{\text{lot C}}) \leq -0.176 \text{ or } (\mu_{\text{lot A}} - \mu_{\text{lot C}}) \geq 0.176 \text{ or} \\ (\mu_{\text{lot B}} - \mu_{\text{lot C}}) \leq -0.176 \text{ or } (\mu_{\text{lot B}} - \mu_{\text{lot C}}) \geq 0.176$$

vs.

$$H_1: (\mu_{\text{lot A}} - \mu_{\text{lot B}}) > -0.176 \text{ and } (\mu_{\text{lot A}} - \mu_{\text{lot B}}) < 0.176 \text{ and} \\ (\mu_{\text{lot A}} - \mu_{\text{lot C}}) > -0.176 \text{ and } (\mu_{\text{lot A}} - \mu_{\text{lot C}}) < 0.176 \text{ and} \\ (\mu_{\text{lot B}} - \mu_{\text{lot C}}) > -0.176 \text{ and } (\mu_{\text{lot B}} - \mu_{\text{lot C}}) < 0.176$$

Here, H_1 refers to the alternative hypothesis of pairwise equivalence (consistency) transformed to the log₁₀ scale. Accordingly, $\mu_{\text{lot A}}$, $\mu_{\text{lot B}}$, and $\mu_{\text{lot C}}$ denote the means of log₁₀-transformed Day 43 titers of the corresponding lot groups. The lot-to-lot consistency will be claimed if the two-sided 95% CIs of all the three pairwise

comparisons are within the equivalence ranges. Significance level to all these tests is $\alpha = 5\%$, which needs no adjustment for multiplicity as all hypotheses have to be rejected (intersection-union test problem).

For CBER criteria HI antibody titer $\geq 1:40$ should meet or exceed 70% and 60% respectively for the two different age cohorts (18- <65 years of age and ≥ 65 years of age) the following hypothesis will be tested:

$$H_0: (\pi_i - \pi_0) \leq 0 \quad \text{vs.} \quad H_1: (\pi_i - \pi_0) > 0$$

Here, H_1 refers to the alternative hypothesis. π_0 denotes the threshold for proportion of subjects with a HI titer $\geq 1:40$ ($\pi_0=0.7$ for subjects 18 to <65 years of age and $\pi_0=0.6$ for subjects ≥ 65 years of age). Significance levels to these tests is $\alpha = 5\%$ which needs no adjustment for multiplicity as all hypothesis have to be rejected (intersection union problem).

7.4.2.1 Analysis Populations for Co-Primary Objectives

The primary analysis population for testing the null hypotheses above will be the Per Protocol Set (PPS).

7.4.2.2 Statistical Methods for Co-Primary Objectives

Log-normal distributed data

All statistical analyses for HI will be performed on the logarithmically (base 10) transformed values. Individual HI titers below detection limit will be set to half that limit.

Geometric mean HI antibody titers (GMT)

Adjusted estimates of geometric mean titers (GMTs), and their associated 95% CIs at Day 43 will be determined using analysis of covariance (ANCOVA) with factors for lot, age groups (18-64, ≥ 65), center and a covariate for the effect defined by the log-transformed prevaccination antibody titer. Influenza-antibody GMTs (Day 43), associated two-sided 95% CIs and median, minimal, and maximal area/titer values will be determined and presented together with N (number of subjects), by lot (for the first primary objective) . This model will include only immunogenic data from the 3 lots of aH5N1.

Statistical analyses will be performed on the logarithmically (base 10) transformed titer values, while median, minimum, and maximum values will be obtained on the actual titer values.

To assess equivalence of lots, the limit of the 95% CI will be compared with the pre-specified thresholds (see [Section 7.2.1](#)).

Analysis of binary data

Binary data (proportion of subjects with HI titer $\geq 1:40$) will be analyzed using loglinear models with a factor for dose group adjusted for center, at Day 43. Proportions and two-sided 95% CIs will be calculated based on these models. Models might be simplified in case of convergence problems.

Handling of missing values for Immunogenicity Data

For immunogenicity data, it may be reasonable to consider missing immunogenicity values as missing completely at random (MCAR), i.e., not informative. Therefore, the primary analysis will comprise a complete case analysis only, without introducing any bias. Imputation methods will not be used.

7.4.2.3 Sample Size and Power Considerations of Co-Primary Objectives

Data observed in previous studies in similar sets (V89_04 in subjects 18-64 years of age; V89_13 in subjects > 65 years of age) showed a variability of the post vaccination titers ranging from 0.75 to 0.88 (in the log scale). With the proposed sample size, assuming a standard deviation of 0.85 for the log₁₀ antibody titers (for each vaccine lot), approximate pairwise equivalence of factor 1 and independency, a single equivalence test based on 718 subjects per lot group has a power of 95%. The resulting overall power is approximately 86%, because the total number of comparisons is three. To account for dropouts (approximately 10%), a total of $n=798$ per lot should be recruited.

Data observed in previous studies in similar populations (V89_04 in subjects 18- <65 years of age; V89_13 in subjects > 65 years of age) showed a proportion of 86% of subjects aged 18 to <65 years and a proportion of 81% of subjects aged 65 years and older achieving an HI antibody titer of $\geq 1:40$. With a sample size of 1077 evaluable subjects from the pooled lots there is an overall power of approximately 98% to achieve the CBER criteria (HI antibody titer $\geq 1:40$ for at least 70% of the subjects aged 18 to <65 years, and for at least 60% of the subjects aged 65 years and older). To account for dropouts (approximately 10%), a minimum sample size of $n=1197$ for all lots combined are needed.

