7.2 Success Criteria

7.2.1 Success Criteria for Co-Primary Objectives

Lot-to-lot consistency, derived from Day 43 HI titers for each aH5N1c lot, will be claimed if, for subjects ≥ 18 years of age in the Per Protocol Set, the two-sided 95% confidence intervals (CIs) of all the three pairwise comparisons (GMT(Group A)/ GMT(Group B), GMT(Group A)/ GMT(Group C), GMT(Group C)/ GMT(Group B)) fall within 0.667 and 1.5. Significance level to all these tests is $\alpha = 5\%$, which needs no adjustment for multiplicity as all hypotheses have to be rejected (intersection-union test problem).

Furthermore after lot-to-lot consistency is achieved, CBER criteria for the percentage of subjects with HI titer $\geq 1:40$ on Day 43 will be assessed as below, for subjects from both age cohorts (18 to 65 years of age and ≥ 65 years of age) on pooled lots. The overall power to fulfill those CBER criteria is 98%.

Immunogenicity according to CBER in subjects 18 - < 65 years of age

The aH5N1c vaccines immunogenicity will be evaluated in subjects 18 to < 65 years of age, using the following measurements according to the current CBER criteria for the adult population (CBER 2007):

- The lower bound of the adjusted two-sided 95% CI for the percentage of subjects achieving an HI antibody titer $\geq 1:40$ should meet or exceed 70%.

Immunogenicity according to CBER in subjects ≥ 65 years of age

The aH5N1c vaccine immunogenicity will be evaluated in subjects ≥ 65 years of age, using the following measurements according to the current CBER criteria for the ≥ 65 years of age population (CBER 2007):

- The lower bound of the adjusted two-sided 95% CI for the percentage of subjects achieving an HI antibody titer $\geq 1:40$ should meet or exceed 60%.

The study will be considered a success if both lot-to-lot consistency for subjects aged ≥ 18 years, and CBER criteria (titer above 1:40) for both age cohorts (18-65 years and ≥ 65 years) are met.

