**1.5 Signature**

	1	2	3	4	5	6	7	8	9	10	11	12
Test significance levels, $\alpha$ (one-sided)	0.025	0.025	0.025	0.025	0.025	0.025	0.025	0.025	0.025	0.025	0.025	0.025
Lower equivalence limit for $\mu_1 - \mu_2, \Delta_L$	-0.176	-0.176	-0.176	-0.176	-0.176	-0.176	-0.176	-0.176	-0.176	-0.176	-0.176	-0.176
Upper equivalence limit for $\mu_1 - \mu_2, \Delta_U$	0.176	0.176	0.176	0.176	0.176	0.176	0.176	0.176	0.176	0.176	0.176	0.176
Expected difference, $\mu_1 - \mu_2$	0.000	0.000	0.000	0.000	0.000	0.000	0.041	0.041	0.041	0.041	0.041	0.041
Common standard deviation, $\sigma$	0.650	0.700	0.750	0.800	0.850	0.880	0.650	0.700	0.750	0.800	0.850	0.880
Power (%)	95	95	95	95	95	95	95	95	95	95	95	95
n per group	421	488	560	636	718	770	604	700	804	914	1032	1106

Novartis Vaccines  
Documentation of Sample Size Calculation

Confidential

Page 5  
V89\_18

One group $\chi^2$ test that proportion equals user specified value (normal approximation)						
	1	2	3	4	5	
Test significance level, $\alpha$	0,050		0,050			
1 or 2 sided test?	2		2			
Null hypothesis proportion, $\pi_0$	0,700		0,600			
Alternative proportion, $\pi_A$	0,860		0,810			
Power ( % )	99		99			
n	1077		1077			

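### Overall lot-consistency power of about 86% is a product for independent comparisons (joint power is about 88%), and the SAP's check of the CBER criterion used a more lenient level than the decision rule

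*Protocol*

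**What the plan says.** **Lot consistency: rule and level.** Protocol section 7.2.1 claims consistency if "the two-sided 95% confidence intervals (CIs) of all the three pairwise comparisons" of the Day 43 GMTs "fall within 0.667 and 1.5". On the log10 scale the margin is ±0.176. Section 7.4.2 continues with "Significance level to all these tests is" 5%, without saying whether that is one- or two-sided. SAP section 11.2 and the hypotheses section of SAP Appendix A repeat this.

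**Lot consistency: power.** Protocol section 7.4.2.3 works from 718 evaluable subjects per lot, "assuming a standard deviation of 0.85 for the" log10 titers, and a true ratio of 1 with what it calls independency. It reports 95% for a single test and then: "The resulting overall power is approximately 86%, because the total number of comparisons is three". The same statement stands in the protocol synopsis and in both parts of SAP Appendix A (20.1 and 20.2). The sizing table in 20.1 has a row headed "Test significance levels", marked one-sided, with 0.025 throughout. The review in 20.2 also lists alpha 0.025 for the lot test.

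**CBER criterion.** The rule in protocol 7.2.1 and SAP 11.2 is that the lower bound of the two-sided 95% CI for the share with HI titer of at least 1:40 reaches 70% (18 to <65 years) or 60% (65 years and over). The sizing run in Appendix A, 20.1 uses a two-sided test at 0.05. The check in 20.2 uses an exact test with one side and nominal alpha 0.05, and reports upper critical values of 780 and 674 for n = 1077.

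**The concern.** The only reason given for going from 95% to 86% is that there are three comparisons, which points to multiplying three single-test powers. With three lots there are only three means. The contrasts A−B, A−C and C−B are tied together, since (A−B) = (A−C) + (C−B), so the product does not give the probability that all three succeed.

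The CBER check matters for a different reason. A second calculation is meant to confirm that the test the trial will run has the claimed power. If it uses a looser level than the decision rule, it confirms the power of a different test. A stated level of 5% without sidedness makes that slip easy to miss, because 5% can mean either one-sided 5% tests (90% intervals) or the two-sided label of a 95% interval.

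**Working it through.** **Inputs.** n = 718 per lot, SD 0.85, true difference 0 (protocol 7.4.2.3); margin 0.176 (protocol 7.4.2); two-sided 95% CIs (protocol 7.2.1), i.e. one-sided 0.025 per bound, as in the SAP Appendix A table; 10% dropout; equal lots.

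**1. The plan's single-test power.**
- SE of a difference = 0.85 × √(2/718) = 0.0449.
- The interval lies inside the margins when the observed difference is smaller in size than 0.176 − 1.96 × 0.0449 = 0.0880.
- Power = 2Φ(0.0880/0.0449) − 1 = 2Φ(1.96) − 1 = 95.0%.
- 718/0.9 = 797.8, so 798 per lot.

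Both planning figures reproduce. They do so only at one-sided 0.025: at one-sided 0.05, 607 per lot would already give 95%, and 718 would give 97.7%.

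**2. The plan's overall power.** 0.95³ = 0.857, the stated 86%. The Bonferroni bound, 1 − 3 × 0.05, would give 85%.

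**3. Joint power.** The pairwise contrasts have correlations of ±0.5, and any two determine the third. With a common SE, all three intervals lie inside the margins exactly when the range of the three lot means is below 0.0880.
- SE of one lot mean = 0.85/√718 = 0.0317, so the limit is w = 0.0880/0.0317 = 2.77.
- P(range of three standard normals < w) = 3∫φ(x)[Φ(x + w) − Φ(x)]² dx = 0.878 to 0.879, depending on whether t or normal quantiles are used.
- Simulation with 2 million replicates agrees: 0.879 with pooled variance, 0.878 with pairwise variances.

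Joint power is therefore about 88%. A joint power of 86% would need about 696 per lot.

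**4. Sensitivity to the SD.** The plan reports SDs from 0.75 to 0.88 in earlier studies. Joint power at 718 per lot:

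| SD | Joint power |
|---|---|
| 0.75 | 97% |
| 0.80 | 93% |
| 0.85 | 88% |
| 0.88 | 84% |

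**5. Type I error of the lot rule.** Each pairwise equivalence test has level 2.5%. For the joint rule at 718 per lot, the error is 2.0% with two lots exactly at the margin and the third midway, and 0.5% with the third equal to one of them.

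**6. CBER check, n = 1077.** Exact binomial upper tails at the null proportion, and exact (Clopper-Pearson) lower 95% bounds:

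| Null | Responders | Upper tail | Exact lower bound |
|---|---|---|---|
| 0.70 | 780 (SAP check) | 0.0435 | 69.6% |
| 0.70 | 783 | 0.0278 | 69.9% |
| 0.70 | 784 | 0.0238 | 70.03% |
| 0.60 | 674 (SAP check) | 0.0444 | 59.6% |
| 0.60 | 678 | 0.0254 | 59.99% |
| 0.60 | 679 | 0.0219 | 60.08% |

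The SAP's 780 and 674 reproduce at one-sided 0.05, but their exact 95% lower bounds fall short of 70% and 60%. The rule needs 784 and 679. At the assumed 86% and 81%, the expected counts are 0.86 × 1077 = 926 and 0.81 × 1077 = 872, far above either set of cut-offs, so power exceeds 99.9% in every case.

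**The case against.** **The power figure is harmless.** It is given as approximate, misses by about 2 points, and understates the power. This stands. The SD alone moves joint power between 84% and 97%, and 88% is itself conditional on SD 0.85, identical lots and an unadjusted comparison, whereas the planned analysis is an ANCOVA with age group, center and baseline titer. None of this makes the product the right calculation for three contrasts of three means.

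**The level is not wrong.** A reader might infer that the tests run at 2.5% while the protocol claims 5%, so that there is a hidden error in alpha or in the sizing. The documents do not support that. The 5% stands beside a two-sided 95% CI rule and reads naturally as its two-sided label, and both lot calculations in SAP Appendix A use 0.025. Rule and sizing agree; only the label is incomplete.

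**The word independency may be correct.** It sits in the clause about the single test, where it can mean that the lot groups are independent, which is a needed assumption. It should be clarified rather than struck out.

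**The CBER mismatch is a separate matter.** A reader might infer that it came from the same ambiguity about 5%. Nothing in the documents shows why the check was set up as it was, and the sizing run in Appendix A, 20.1 used two-sided 0.05, which fits the rule. It is also fair that 784 and 679 are exact-interval cut-offs, while the plan uses model-based intervals adjusted for center. Wald intervals give 783 and 678, and Wilson intervals 784 and 678, so the difference is about one responder. The mismatch with 780 and 674 remains under all three.

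**Conclusion.** Wrong as written, but minor. Two corrections stand.

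- The overall lot-consistency power under the plan's own assumptions is about 88%, not the 86% obtained by multiplying three dependent comparisons as if they were independent. The misstatement is slightly conservative.
- The CBER check in SAP Appendix A, 20.2 verified a more lenient rule than the trial applies, by 4 responders (784 − 780) in the younger cohort and 5 (679 − 674) in the older one. This has no practical effect on power.

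It would be too strong to conclude that the trial is underpowered, that type I error is inflated, or that 718 per lot was derived for the wrong test: the sizing reproduces at exactly the level the decision rule implies.

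The 88% rests on SD 0.85, three lots with identical true GMTs, 718 evaluable per lot and no covariate adjustment. The assumption of identical lots matters more than the correlation. If the largest true lot ratio is 1.1, a case the sizing table includes, joint power at 718 per lot is about 74% to 77%, depending on where the third lot lies.

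**What to change.** 1. In the protocol synopsis, protocol 7.4.2.3 and both parts of SAP Appendix A, give the overall lot-consistency power as about 88%, allowing for the correlation between comparisons. Alternatively, keep 86% and describe it as a conservative approximation that ignores that correlation.
2. In the same places, say that independency refers to the lot groups and not to the three comparisons.
3. In protocol 7.2.1 and 7.4.2 and SAP 11.2, label the 5% as two-sided, equal to one-sided 2.5% per test. Carry the label into the synopsis and the hypotheses section of Appendix A.
4. Rerun the CBER check in Appendix A, 20.2 at one-sided 0.025 and replace 780 and 674 with the resulting cut-offs (784 and 679 for the exact test), noting that the model-based interval may shift them by about one responder.

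The cost is a few sentences and one short rerun. Sample size, decision rule and control of type I error stay as they are.
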